### **Pharmaceutical Data**

Ipilimumab is a sterile, preservative-free, clear to slightly opalescent, colorless to pale yellow solution for intravenous infusion, which may contain a small amount of visible translucent-to-white, amorphous ipilimumab particulates. It is supplied in single-use vials of 50 mg/10 mL and 200 mg/40 mL. Each milliliter contains 5 mg of ipilimumab.

### **Supply**

Ipilimumab is commercially available.

### **Specific Risk/Adverse Events with ipilimumab**

Ipilimumab can result in severe and fatal immune-mediated adverse reactions due to T-cell activation and proliferation. These immune-mediated reactions may involve any organ system; however, the most common severe immune-mediated adverse reactions are enterocolitis, hepatitis, dermatitis (including toxic epidermal necrolysis), neuropathy, and endocrinopathy. The majority of these immune-mediated reactions initially manifested during treatment; however, a minority occurred weeks to months after discontinuation of ipilimumab.

Permanently discontinue ipilimumab and initiate systemic high-dose corticosteroid therapy for severe immune-mediate reactions. Assess patients for signs and symptoms of enterocolitis, dermatitis, neuropathy, and endocrinopathy and evaluate clinical chemistries including liver function tests and thyroid function tests at baseline and before each dose. For specific details of toxicity management, the treating physician is instructed to refer to the package insert for ipilimumab and to follow the instructions and algorithms therein.

Specific attention to development of autoimmune events during periodic study visits can be evaluated by an optional checklist provided in **Appendix E**. This checklist in addition to the serologic tests obtained can be used by the study physicians to determine if further evaluation for autoimmune disease is warranted by an appropriate specialist in the organ system affected. This can be done to avoid misinterpretation of spurious autoimmune test results.

Trials using immunomodulatory agents such as ipilimumab CTLA-4 have shown a correlation between disease response and so called autoimmune breakthrough events (ABEs) like hypophysitis, colitis, autoimmune hepatitis, or dermatitis. It is for this reason that they are distinguished from other adverse events.

### 5.3 Nivolumab (Opdivo)

#### Description

Binding of the PD-1 ligands, PD-L1 and PD-L2, to the PD-1 receptor found on T cells, inhibits T-cell proliferation and cytokine production. Upregulation of PD-1 ligands occurs in some tumors and signaling through this pathway can contribute to inhibition of active T-cell immune surveillance of tumors. Nivolumab is a human immunoglobulin G4 (IgG4) monoclonal antibody that binds to the PD-1 receptor and blocks its interaction with PD-L1 and PD-L2, releasing PD-1 pathway-mediated inhibition of the immune response, including the anti-tumor immune response. Nivolumab is an IgG4 kappa immunoglobulin that has a calculated molecular mass of 146 kDa.

#### Pharmacokinetics

The pharmacokinetics (PK) of nivolumab was studied in patients over a dose range of 0.1 to 20 mg/kg administered as a single dose or as multiple doses of nivolumab every 2 or 3 weeks. Based on a population pharmacokinetic (PK) analysis using data from 909 patients, the geometric mean (% coefficient of variation [CV%]) clearance (CL) is 9.5 mL/h (49.7%), geometric mean volume of distribution at steady state ( $V_{ss}$ ) is 8.0 L (30.4%), and geometric mean elimination half-life ( $t_{1/2}$ ) is 26.7 days (101%). Steady-state concentrations of nivolumab were reached by 12 weeks when administered at 3 mg/kg every 2 weeks, and systemic accumulation was approximately 3-fold. The exposure to nivolumab increased dose proportionally over the dose range of 0.1 to 10 mg/kg administered every 2 weeks.

*Specific Populations:* Based on a population PK analysis using data from 909 patients, the clearance of nivolumab increased with increasing body weight supporting a weight-based dose. The population PK analysis suggested that the following factors had no clinically important effect on the clearance of nivolumab: age (29 to 87 years), gender, race, baseline LDH, PD-L1 expression, tumor type, tumor size, renal impairment, and mild hepatic impairment.

*Renal Impairment:* The effect of renal impairment on the clearance of nivolumab was evaluated by a population PK analysis in patients with mild (eGFR 60 to 89 mL/min/1.73 m^2; n=313), moderate (eGFR 30 to 59 mL/min/1.73 m^2; n=140), or severe (eGFR 15 to 29 mL/min/1.73 m^2; n=3) renal impairment. No clinically important differences in the clearance of nivolumab were found between patients with renal impairment and patients with normal renal function.

*Hepatic Impairment:* The effect of hepatic impairment on the clearance of nivolumab was evaluated by population PK analyses in patients with mild hepatic impairment (total bilirubin [TB] less than or equal to the upper limit of normal [ULN] and AST greater than ULN or TB less than 1 to 1.5 times ULN and any AST; n=92). No clinically important differences in the clearance of nivolumab were found between patients with mild hepatic impairment and patients with normal hepatic function. Nivolumab has not been studied in patients with moderate (TB greater than 1.5 to 3 times ULN and any AST) or severe impairment (TB greater than 3 times ULN and any AST).

#### Pharmaceutical Data

Nivolumab is a clear to opalescent, colorless to pale-yellow solution. Discard the vial if the solution is cloudy, is discolored, or contains extraneous particulate matter other than a few translucent-to-white, proteinaceous particles. Do not shake the vial. It is supplied in 40 mg/4 mL (10 mg/mL) and 100 mg/10 mL (10 mg/mL) solution in single-use vials.

**Supply**

Nivolumab is commercially available.

**Specific Risk/Adverse Events**

Nivolumab can cause severe and fatal immune mediated adverse effects. Many organs systems can be involved. The most common severe adverse events include pneumonitis, colitis, hepatitis, nephritis, and thyroid disease (either hypothyroidism or hyperthyroidism). Additional immune mediated reactions observed include adrenal insufficiency, pancreatitis, neuropathies, hypophysitis, and Guillain-Barre syndrome.

Management of these conditions includes withholding of nivolumab, administration of high-dose corticosteroids, and if appropriate, initiation of hormone replacement therapy.

**5.4 Pembrolizumab (Keytruda)****Description**

Pembrolizumab is a humanized monoclonal antibody that blocks the interaction between PD-1 and its ligands, PD-L1 and PD-L2. Pembrolizumab is an IgG4 kappa immunoglobulin with an approximate molecular weight of 149 kDa. Binding of the PD-1 ligands, PD-L1 and PD-L2, to the PD-1 receptor found on T cells, inhibits T cell proliferation and cytokine production. Upregulation of PD-1 ligands occurs in some tumors and signaling through this pathway can contribute to inhibition of active T-cell immune surveillance of tumors. Pembrolizumab is a monoclonal antibody that binds to the PD-1 receptor and blocks its interaction with PD-L1 and PD-L2, releasing PD-1 pathway-mediated inhibition of the immune response, including the anti-tumor immune response.

**Pharmacokinetics**

The pharmacokinetics of pembrolizumab was studied in 479 patients who received doses of 1 to 10 mg/kg every 2 weeks or 2 to 10 mg/kg every 3 weeks. Based on a population pharmacokinetic analysis, the mean [% coefficient of variation (CV%)] clearance (CL) is 0.22 L/day (28%) and the mean (CV%) elimination half-life (t1/2) is 26 days (24%). Steady-state concentrations of pembrolizumab were reached by 18 weeks of repeated dosing with an every 3-week regimen and the systemic accumulation was 2.1-fold. The peak concentration (Cmax), trough concentration (Cmin), and area under the plasma concentration versus time curve at steady state (AUCss) of pembrolizumab increased dose proportionally in the dose range of 2 to 10 mg/kg every 3 weeks.

*Specific Populations:* The effects of various covariates on the pharmacokinetics of pembrolizumab were assessed in population pharmacokinetic analyses. The CL of pembrolizumab increased with increasing body weight; the resulting exposure differences were adequately addressed by the administration of a weight-based dose. The following factors had no clinically important effect on the CL of pembrolizumab: age (range 18 to 94 years), gender, renal impairment, mild hepatic impairment, and tumor burden. The effect of race could not be assessed due to limited data available in non-White patients.

*Renal Impairment:* The effect of renal impairment on the CL of pembrolizumab was evaluated by population pharmacokinetic analyses in patients with mild (eGFR 60 to 89 mL/min/1.73 m^2;

n=210), moderate (eGFR 30 to 59 mL/min/1.73 m^2; n=43), or severe (eGFR 15 to 29 mL/min/1.73 m^2; n=2) renal impairment compared to patients with normal (eGFR greater than or equal to 90 mL/min/1.73 m^2; n=221) renal function. No clinically important differences in the CL of pembrolizumab were found between patients with renal impairment and patients with normal renal function.

*Hepatic Impairment:* The effect of hepatic impairment on the CL of pembrolizumab was evaluated by population pharmacokinetic analyses in patients with mild hepatic impairment (TB less than or equal to ULN and AST greater than ULN or TB between 1 and 1.5 times ULN and any AST; n=59) compared to patients with normal hepatic function (TB and AST less than or equal to ULN; n=410). No clinically important differences in the CL of pembrolizumab were found between patients with mild hepatic impairment and normal hepatic function. Pembrolizumab has not been studied in patients with moderate (TB greater than 1.5 to 3 times ULN and any AST) or severe (TB greater than 3 times ULN and any AST) hepatic impairment.

### **Pharmaceutical Data**

Pembrolizumab for injection is a sterile, preservative-free, white to off-white, lyophilized powder in single-use vials. Each vial is reconstituted and diluted for intravenous infusion. Each 2 mL of reconstituted solution contains 50 mg of pembrolizumab and is formulated in L-histidine (3.1 mg), polysorbate 80 (0.4 mg), and sucrose (140 mg). May contain hydrochloric acid/sodium hydroxide to adjust pH to 5.5.

### **Supply**

Pembrolizumab is commercially available.

### **Specific Risks / Adverse Events**

Pembrolizumab can cause severe immune mediated adverse events and can involve multiple organ systems. Severe immune mediated adverse events include pneumonitis, colitis, hepatitis, hypophysitis, nephritis, and hypothyroidism and hyperthyroidism. Additional severe immune mediated adverse events can include dermatitis, uveitis, myositis, pancreatitis, and adrenal insufficiency.

For suspected immune-mediated adverse reactions, ensure adequate evaluation to confirm etiology or exclude other causes. Based on the severity of the adverse reaction, withhold pembrolizumab and administer corticosteroids.

## **6 DOSING DELAYS/DOSE MODIFICATIONS**

The dosing delay and modification information contained in this section concerning ipilimumab, nivolumab, and pembrolizumab is provided for background purposes. Dosing delays and / or modification of these agents should be performed consistent with standard of care practice by the treating physician within the guidelines provided in the respective package inserts.

### **6.1 Dosing Delays**

A significant number of patients entered into clinical trials at the clinical sites live outside of the area including patients referred from across the United States. Due to potential scheduling or travel

difficulties, unrelated intercurrent illness, patient social or employment issues, weekends, government and other holidays, treatments may not be able to be administered on the planned protocol schedule. Study visits may be performed +/- 3 days from the targeted study visit date to allow for holidays and other scheduling conflicts.

### **6.2 Dorgenmeltucel-L (HyperAcute-Melanoma) Dose Modifications**

There is no provision made in this protocol for the reduction of the dose or other dosing modification of the immunotherapy treatment.

### **6.3 Ipilimumab Dose Modifications**

The administration of ipilimumab under this protocol is to be within accordance with the package insert for ipilimumab. This includes toxicity management and dosing adjustments or discontinuation of ipilimumab. The following is intended to highlight aspects of management.

- Ipilimumab related toxicities must be resolved to baseline or  $\leq$  Grade 1 prior to administering the next dose.
- No dose reductions for ipilimumab are allowed.
- Ipilimumab can be delayed if the reason for the delay is toxicity/AE and if resolved to Grade 1 or better can restart and continue every 3 weeks until all 4 planned doses are administered or 16 weeks from first dose, whichever occurs earlier.
- Please refer to the AE management algorithms provided by the package insert for ipilimumab on management of potentially ipilimumab-related adverse events (also in **Appendix D**).
- Liver function tests (AST, ALT total bilirubin) will be evaluated for every subject prior to administration of ipilimumab. Blood samples must be collected and analyzed within 3 days prior to dosing. Liver function test results must be reviewed by the principal investigator or designee prior to ipilimumab administration and meet dosing criteria specifications:
  - $< 2.5 \times$  ULN for AST and ALT and  $< 1.5 \times$  ULN for total bilirubin
- If abnormal LFT values are detected, the subject must be managed using hepatotoxicity algorithm (see **Appendix D**).

Treatment may resume when the AE(s) resolve(s) to Grade 1 or baseline value.

During ipilimumab administration, ipilimumab must be permanently discontinued if the subject experiences any of the following toxicities. Events requiring permanent discontinuation are:

- Grade 3 or 4 motor or sensory neuropathy, regardless of causality
- Any AE which, in the judgment of the investigator, presents a substantial clinical risk to the subject with investigational drug dosing.
- Any  $\geq$  Grade 2 eye pain or reduction of visual acuity that does not respond to topical therapy and does not improve to Grade 1 or better severity with topical therapy or requires systemic treatment.
- Any other  $\geq$  Grade 3 non-skin related AE with the exception of laboratory abnormalities and Grade 3 nausea and vomiting.
- Any Grade 4 laboratory abnormalities
- Persistent Grade 2 adverse reactions (that push ipilimumab administration beyond the

16 week window from first dose) or inability to reduce corticosteroid dose to 7.5 mg prednisone or equivalent per day.

- Severe or life-threatening adverse reactions, including any of the following:
  - Colitis with abdominal pain, fever, ileus, or peritoneal signs; increase in stool frequency ( $\geq$  Grade 3)
  - AST or ALT  $>$  5 times the ULN or total bilirubin  $>$  3 times the ULN
  - Stevens-Johnson syndrome, toxic epidermal necrolysis, or rash complicated by full thickness dermal ulceration, or necrotic, bullous or hemorrhagic manifestations.
  - Severe motor or sensory neuropathy, Guillain-Barre syndrome, or myasthenia gravis.
  - Severe immune-mediated reactions involving any organ system (e.g. nephritis, pneumonitis, pancreatitis, myocarditis).
  - Severe infusion reaction (see Section 6.4)

#### **6.4 Nivolumab Dosing Modifications**

There are no recommended dose modifications for hypothyroidism or hyperthyroidism. Immune mediated adverse events should be treated with corticosteroids in accordance with the guidelines in the package insert.

Withhold nivolumab for any of the following:

- Grade 2 pneumonitis
- Grade 2 or 3 colitis
- Aspartate aminotransferase (AST) or alanine aminotransferase (ALT) greater than 3 and up to 5 times upper limit of normal (ULN) or total bilirubin greater than 1.5 and up to 3 times ULN
- Creatinine greater than 1.5 and up to 6 times ULN or greater than 1.5 times baseline
- Any other severe or Grade 3 treatment-related adverse reactions

Resume nivolumab in patients whose adverse reactions recover to Grade 0 to 1.

Permanently discontinue nivolumab for any of the following:

- Any life-threatening or Grade 4 adverse reaction
- Grade 3 or 4 pneumonitis
- Grade 4 colitis
- AST or ALT greater than 5 times ULN or total bilirubin greater than 3 times ULN
- Creatinine greater than 6 times ULN
- Any severe or Grade 3 treatment-related adverse reaction that recurs
- Inability to reduce corticosteroid dose to 10 mg or less of prednisone or equivalent per day within 12 weeks
- Persistent Grade 2 or 3 treatment-related adverse reactions that do not recover to Grade 1 or resolve within 12 weeks after last dose of nivolumab

#### **6.5 Pembrolizumab Dosing Modifications**

For immune mediated adverse reactions administer corticosteroids based on the severity of the reaction. See package insert for guidelines.

Withhold pembrolizumab for any of the following:

- Grade 2 pneumonitis
- Grade 2 or 3 colitis
- Symptomatic hypophysitis
- Grade 2 nephritis
- Grade 3 hyperthyroidism
- Aspartate aminotransferase (AST) or alanine aminotransferase (ALT) greater than 3 and up to 5 times upper limit of normal (ULN) or total bilirubin greater than 1.5 and up to 3 times ULN
- Any other severe or Grade 3 treatment-related adverse reaction

Resume pembrolizumab in patients whose adverse reactions recover to Grade 0-1.

Permanently discontinue pembrolizumab for any of the following:

- Any life-threatening adverse reaction
- Grade 3 or 4 pneumonitis
- Grade 3 or 4 nephritis
- AST or ALT greater than 5 times ULN or total bilirubin greater than 3 times ULN
- For patients with liver metastasis who begin treatment with Grade 2 AST or ALT, if AST or ALT increases by greater than or equal to 50% relative to baseline and lasts for at least 1 week
- Grade 3 or 4 infusion-related reactions
- Inability to reduce corticosteroid dose to 10 mg or less of prednisone or equivalent per day within 12 weeks
- Persistent Grade 2 or 3 adverse reactions that do not recover to Grade 0-1 within 12 weeks after last dose of pembrolizumab
- Any severe or Grade 3 treatment-related adverse reaction that recurs

## ***6.6 Treatment of Checkpoint Inhibitor Related Infusion Reaction***

Infusion reactions should be graded according to CTCAE version 4.03 Allergic reaction/hypersensitivity criteria.

Severe infusion reaction requires permanent discontinuation for further treatment.

Appropriate medical therapy including fluids, epinephrine, corticosteroids, IV antihistamines, bronchodilators, and oxygen should be available for use in the treatment of such reactions.

In each case of an infusion reaction, the investigator should institute treatment measures according to the best available medical practice.

## **7 CORRELATIVE/SPECIAL STUDIES**

### **7.1 *Parameters measured at baseline to evaluate subject's general immunological status***

[REDACTED]

### **7.2 *Immunological monitoring during treatment and follow-up***

[REDACTED]

### 8 STUDY CALENDARS

#### Study Calendar for Arm 1A (Ipilimumab plus Dorgenmeltucel-L Immunotherapy)

Ipilimumab 3 mg/kg IV given Q3 weeks x 4, dorgenmeltucel-L continues for up to 24 immunizations. Study visits may be performed +/- 3 days from the targeted study visit date to allow for holidays and other scheduling conflicts. Follow-up visits may be performed +/- 2 weeks from the targeted study visit date.

EVALUATIONS	Pre-Study DAY	Wk 1	Wk 2	Wk 3	Wk 4	Wk 5	Wk 6	Wk 7	Wk 8	Wk 9	Wk 10	Wk 11	Wk 12	Wk 13	Wk 14	Wk 16	Wk 18	Wk 20	Wk 22	Wk 24	Mo 7	Mo 8	Mo 9	Mo 10	Mo 11	Mo 12	Mo 15	Mo 18	Mo 21	Mo 24	1ST FUV						
HAM Injections		A	A	A	A		A		A		A		A		A	A	A	A	A	A	A	A	A	A	A	A	A	A	A	A	A						
Ipilimumab				X				X			X			X																							
Informed consent	X																																				
Demographics	X																																				
Medical history	X																																				
Concurrent meds	X																																				
Physical exam	X	X			X			X			X			X		X		X		X	-----Complete per SOC-----																X
Vital signs	X	X	X	X	X		X	X	X		X		X	X	X	X	X	X	X	X	X	X	X	X	X	X	X	X	X	X	X	X					
Height	X																																				
Weight	X	X			X			X			X			X		X		X		X	X	X	X	X	X	X	X	X	X	X	X	X					
Performance status	X	X			X			X			X			X		X		X		X	X	X	X	X	X	X	X	X	X	X	X	X					
CBC w/diff, plts	X	X			X			X			X			X		X		X		X	X	X	X	X	X	X	X	X	X	X	X	X					
Serum chemistry (with LDH)	B				B			B			B			B		B		B		B	B	B	B	B	B	B	B	B	B	B	B						
b-HCG	C																																				
TSH and Free T4	X				X			X			X			X																							
	E												E							E											E	E					
	F																																				
	H							H						H						H					H		H		H		H	H					
	I			I	I			I			I			I		I				I	I	I	I	I	I	I	I	I	I	I	I	I	I				
	J							J			J																										
Radiologic Tumor (RECIST/iRRC) evaluation	X													X						X			X			X	X	X	X	X	X	X					
AE/SAE Evaluation		-----Evaluate throughout Study and Follow Up Per Protocol-----																																			

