**Protocol Schemas for Arm 1A and Arm 2A**  
**Ipilimumab plus dorgenmeltucel-L - Arm 1A**  
**Ipilimumab Alone – Arm 2A**

Arm 1A: HAM + IPILIMUMAB			
Month	Week	Day	Treatment
	1	1	HAM
	2	8	HAM
	3	15	HAM
1	4	22	HAM + IPI
	5	29	REST
	6	36	HAM
	7	43	IPI
2	8	50	HAM
	9	57	REST
	10	64	HAM + IPI
	11	71	REST
3	12	78	HAM
	13	85	IPI
	14	92	HAM
	Evaluate for Response		
	15	99	REST
4	16	106	HAM
	17	113	REST
	18	120	HAM
	19	127	REST
5	20	134	HAM
	21	141	REST
	22	148	HAM
	23	155	REST
6	24		HAM
	Evaluate for Response		
7			HAM
8			HAM
9			HAM
	Evaluate for Response		
10			HAM
11			HAM
12			HAM
	Evaluate for Response		
15			HAM
	Evaluate for Response		
18			HAM
	Evaluate for Response		
21			HAM
	Evaluate for Response		
24			HAM
	Evaluate for Response		

Arm 2A: IPILIMUMAB ALONE		
Week	Day	Treatment
1	1	IPI
2	8	REST
3	15	REST
4	22	IPI
5	29	REST
6	36	REST
7	43	IPI
8	50	REST
9	57	REST
10	64	IPI
11	71	REST
12	78	REST
	Evaluate for Response	

IPI Alone Group: After treatment, observe for disease progression. If disease progresses, subjects go off study but will continue to be followed for survival status.

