**Study Calendar for Arm 2A (Ipilimumab Alone)**

Ipilimumab 3 mg/kg IV given Q3 weeks x 4, then evaluate disease. Study visits may be performed +/- 3 days from the targeted study visit date to allow for holidays and other scheduling conflicts. Follow-up visits may be performed +/- 2 weeks from the targeted study visit date.

EVALUATIONS	Pre-Study	Wk 1	Wk 2	Wk 3	Wk 4	Wk 5	Wk 6	Wk 7	Wk 8	Wk 9	Wk 10	Wk 11	Wk 12	Wk 13	1ST FUV
		D1	D8	D15	D22	D29	D36	D43	D50	D57	D64	D71	D78	D85	
Ipilimumab		X			X			X			X				
Informed consent	X														
Demographics	X														
Medical history	X														
Concurrent meds	X	X-----X													
Physical exam	X	X			X			X			X				X
Vital signs	X	X			X			X			X			X	X
Height	X														
Weight	X	X			X			X			X				X
Performance status	X	X			X			X			X			X	X
CBC w/diff, plts	X	X			X			X			X			X	X
Serum chemistry (with LDH)	B	B			B			B			B			B	B
B-HCG	C														
TSH and Free T4	X	X			X			X			X			X	
		E												E	E
		H						H							H
		I			I			I			I			I	I
		J						J			J				
Radiologic Tumor (RECIST/iRRC) evaluation	X													X	X
Adverse event evaluation		X-----X													X

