**Follow Up Visits for ALL Subjects (after 1st FUV):**

- Imaging to be completed every 3 months until disease progression, after disease progression imaging is completed per standard of care
- Survival status checks to be completed at least every 3 months until death or lost to follow up
- All other assessments should be completed per standard of care practices.

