**Hospitalization, Prolonged Hospitalization or Surgery**

Any adverse event that results in hospitalization or prolonged hospitalization should be documented and reported as a serious adverse event unless specifically instructed otherwise in this protocol. Any condition responsible for surgery should be documented as an adverse event if the condition meets the criteria for and adverse event.

Neither the condition, hospitalization, prolonged hospitalization, nor surgery are reported as an adverse event in the following circumstances:

- Hospitalization or prolonged hospitalization for diagnostic or elective surgical procedures for a preexisting condition. Surgery should ***not*** be reported as an outcome of an adverse event if the purpose of the surgery was elective or diagnostic and the outcome was uneventful.
- Hospitalization or prolonged hospitalization required to allow efficacy measurement for the study.
- Hospitalization or prolonged hospitalization for therapy of the target disease of the study, unless it is a worsening or increase in frequency of hospital admissions as judged by the clinical investigator.

Routine Adverse Event Reporting

All Adverse Events must be reported in routine study data submissions. AEs reported through expedited SAE reports must also be reported in routine study data submissions (CRFs).

Adverse Event Case Report Form

All adverse events (regardless of grade and attribution) observed while on study and for 30 days after last dose of treatment, must be recorded on the adverse event case report form. After 30 days from last dose of treatment, only adverse events that are related to the study drug/combination are required to be recorded on the adverse event forms.

Reporting Requirements for Baseline Adverse Events:

A pertinent positive finding identified on baseline assessment is to be documented as a Baseline Adverse Event using CTCAE terminology and grade on the provided Baseline CRF. An expedited

AE report is not required if a patient is entered on to the study with a pre-existing condition (e.g., elevated laboratory value, diarrhea). The baseline AE must be re-assessed throughout the trial and reported if it fulfills expedited AE reporting guidelines.

- 1) If the pre-existing condition worsens in severity, the investigator must reassess the event to determine if an expedited report is required.

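### In the ipilimumab stratum, scheduled thyroid testing stops on the day of dose 4 in the vaccine arm but runs 21 days past dose 4 in the control arm; one assay at Arm 1A's existing Week 16 draw aligns them

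*Combined protocol and SAP*

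**What the plan says.** The synopsis schema headed "Ipilimumab plus dorgenmeltucel-L - Arm 1A" gives ipilimumab on Days 22, 43, 64 and 85 in the vaccine arm, after a lead-in of vaccine alone. The schema beside it gives ipilimumab on Days 1, 22, 43 and 64 in Arm 2A, whose Section 8 calendar describes the regimen as "Ipilimumab 3 mg/kg IV given Q3 weeks x 4, then evaluate disease".

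The thyroid row in the two calendars is labelled "TSH and Free T4". In Arm 1A it is marked at pre-study and Weeks 4, 7, 10 and 13, then left blank through Month 24 and the first follow-up visit. In Arm 2A it is marked at pre-study and Days 1, 22, 43, 64 and 85, with nothing at the first follow-up visit. Legend item B, which lists the serum chemistry panel, includes no thyroid test.

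Section 5.2 asks for thyroid function tests at entry and ahead of every ipilimumab dose. It names endocrinopathy among the most common severe immune-mediated reactions and says of such reactions that "a minority occurred weeks to months after discontinuation of ipilimumab". Section 6.1 sets the visit allowance: "Study visits may be performed +/- 3 days from the targeted study visit date to allow for holidays and other scheduling conflicts". After the first follow-up visit, beyond imaging and survival checks, "All other assessments should be completed per standard of care practices".

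**The concern.** Ipilimumab starts three weeks later in Arm 1A than in Arm 2A, yet the thyroid row ends at Week 13 in both calendars. The control arm therefore has a scheduled check three weeks after its last ipilimumab dose, and the investigational arm does not.

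Safety of the combination against checkpoint inhibition alone is a primary objective. Under Section 10.4 an abnormal test becomes an adverse event if, for example, it leads to treatment or further tests, so a scheduled assay can generate a recorded event. Taking scheduled tests alone, a laboratory-only TSH/free T4 change arising after dose 4 could be found in controls and missed in vaccine patients, which could under-count thyroid events in the arm whose safety is in question. There is also a patient-safety side: the protocol itself warns of late reactions, and the arm given the experimental combination has the shorter scheduled thyroid follow-up after its last ipilimumab dose.

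**Working it through.** No sample-size formula applies; this is calendar arithmetic.

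**Inputs.** Dose days come from the synopsis schemas, test visits from the Section 8 calendars for Arms 1A and 2A, and the ±3-day allowance from Section 6.1. Study day = 1 + 7 × (week − 1), so Weeks 4, 7, 10, 13 and 16 are Days 22, 43, 64, 85 and 106.

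**Check of the stated regimen.** Arm 1A: 43 − 22 = 64 − 43 = 85 − 64 = 21. Arm 2A: 22 − 1 = 43 − 22 = 64 − 43 = 21. Both are four doses three weeks apart, as the plan states.

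**Tests relative to ipilimumab, as written.**

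| | Arm 1A | Arm 2A |
|---|---|---|
| Test days after pre-study | 22, 43, 64, 85 | 1, 22, 43, 64, 85 |
| First ipilimumab | Day 22 | Day 1 |
| Days from first ipilimumab | 0, 21, 42, 63 | 0, 21, 42, 63, 84 |
| Dose 4 | Day 85 | Day 64 |
| Last test minus dose 4 | 85 − 85 = 0 | 85 − 64 = 21 |
| Scheduled tests after dose 4 | 0 | 1 |
| Scheduled tests including pre-study | 5 | 6 |

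**With a test added at Arm 1A Week 16.** 106 − 85 = 21 days after dose 4, and 106 − 22 = 84 days from first ipilimumab. Arm 1A becomes 0, 21, 42, 63, 84, identical to Arm 2A, with 6 scheduled tests in each arm. CBC and serum chemistry are already marked at Arm 1A Week 16, so blood is being drawn.

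**Effect of the visit allowance.** With up to 3 days either way at both the dose visit and the test visit:

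- Arm 1A: shortest lag (106 − 3) − (85 + 3) = 15 days; longest (106 + 3) − (85 − 3) = 27 days.
- Arm 2A: shortest (85 − 3) − (64 + 3) = 15 days; longest (85 + 3) − (64 − 3) = 27 days.

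Of the 7 × 7 = 49 whole-day combinations, 3 + 2 + 1 = 6 give a lag above 24 days and none exceeds 27. An analysis window of only 21 + 3 = 24 days would drop some compliant tests.

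**Reading of the table.** The extracted Arm 1A calendar has faults: more columns than headings, the first ipilimumab mark under Week 3, and 25 vaccine marks against 24 stated. The schema places that first dose in Week 4 and, separately, dose 4 on Day 85. The thyroid marks coincide with the schema's four dose days, so these faults do not alter the result.

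**The case against.** The strongest reply is that no rule is broken. Section 5.2 asks for tests at entry and ahead of each dose; both arms comply, and Arm 2A's Day 85 test is one more than required. That is true, and it is why this is an improvement rather than an error. But the protocol schedules that extra check only for patients not receiving the vaccine and gives no reason for the difference.

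Second, the imbalance depends on the clock. By study day both arms share tests on Days 22, 43, 64 and 85, and a Day 106 test in Arm 1A alone would make the last study day unequal. Also true. For a toxicity of ipilimumab, though, time since ipilimumab is the relevant clock.

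Third, overall surveillance may favour Arm 1A. After dose 4 it has examinations and laboratory tests at Weeks 16, 20 and 24 and frequent vaccine visits. Adverse events are recorded when "observed while on study and for 30 days after last dose of treatment", and treatment there includes vaccine. Physicians may test thyroid function locally, and the protocol offers an optional autoimmune checklist. This stands: the net direction of any bias is unknown. Unscheduled and unmatched detection does not replace a common schedule.

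Fourth, spanning text may have been lost from Arm 1A's thyroid row in extraction, since the concurrent-medication row lacks the span seen in the Arm 2A calendar and the Arm 1C thyroid row ends with one. This cannot be excluded outright. However, other spans in the Arm 1A calendar survived, and the Arm 1C span refers to continuing pembrolizumab, which has no counterpart once ipilimumab ends at Week 13.

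Finally, one test at 21 days covers little of a late period measured in weeks to months. That is correct, and the change does not claim otherwise.

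**Conclusion.** The concern holds, as a modest between-arm imbalance confined to protocol-scheduled TSH/free T4 in the ipilimumab stratum: no scheduled test after dose 4 in Arm 1A against one, at 21 days, in Arm 2A. It bears on comparability for a primary safety objective and on individual safety. It invalidates no analysis and does not touch PFS or power.

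The conclusion assumes on-schedule dosing. Section 6.3 lets ipilimumab be delayed for toxicity "until all 4 planned doses are administered or 16 weeks from first dose, whichever occurs earlier", and a delayed dose 4 would shift these lags in either arm. It also assumes that the redacted calendar rows (E, H, I and J) contain no thyroid test. Section 12.3 does not define the on-treatment period for its laboratory shift tables, so whether Arm 2A's Day 85 value would enter them is unknown, and no distortion of a planned table is claimed. The number of patients affected cannot be computed: the documents give neither the size of the ipilimumab stratum nor a late thyroid event rate.

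One mismatch remains after the change: relative to the study calendar, first ipilimumab comes 21 days later in Arm 1A, so the pre-study sample sits further from it.

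**What to change.** Mark TSH and free T4 at Week 16 (Day 106) in the Arm 1A calendar, on the draw that already carries CBC and chemistry. If thyroid results are compared over a window after dose 4, make that window at least 27 days (21 plus 3 at each of the two visits), so that Arm 1A's Day 106 and Arm 2A's Day 85 values are both included. A thyroid test at the first follow-up visit is optional for individual safety, but it does not align the arms.

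The cost is one TSH/free T4 assay per Arm 1A patient, with no new visit and no change to Arm 2A.
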